**Medical Screening:** Participants will be physically healthy **nonsmokers** with a BMI  $\leq 32 \text{ kg/m}^2$ , and no cardiovascular disease other than mild hypertension. Participants will be assessed by history, physical exam, and laboratory tests assessing cardiac, hematopoietic, renal, hepatic, and hormonal function (CBC, CMP, TSH, U/A, ECG), and will have a medical history review and physical examination to establish general physical health. Blood will also be obtained for an **exploratory genetic analysis** to examine APOE and COMT genotypes as these genes have been shown to be important in cognition in older adults. APOE is important for cognitive decline in older adults and associated with cholinergic function (Espeseth et al, 2006). The COMT ValMet polymorphism modulates working memory performance in psychiatric populations (e.g. Meyer-Lindenberg & Weinberger 2006) but not in healthy subjects (Blanchard et al. 2011). However, it affects working memory-related brain activation (Jacobs & D'Esposito 2011).

Depending on the distribution of genotypes we will use this information as a covariate in the imaging analysis described below.

Once a participant passes the screening, s/he will be scheduled for **3 challenge and fMRI study days**.

**Pharmacological Challenges:** These procedures used for the nAChR challenges are similar to the procedures used in our prior studies ([name] et al. 2008; 2010; 2012; Carstens et al. 2011; [name] et al. 2009; 2012). The nAChR antagonist mecamylamine (**MECA**) will be administered at a dose of 20 mg orally as the hydrochloride salt. Placebos will consist of identical capsules filled with lactose. This dose of MECA is the same dose used in our prior studies in older women ([name] et al. 2008; 2012). Nicotine (**NIC**) will be administered with a 7 mg patch placed on the back of the shoulder for 45 minutes. Matching placebo patches will be used. This dosing procedure has utilized at UVM for many years to study the acute effects of nicotine in nonsmokers (Carstens et al. 2011; [name] et al. 2009; 2012). One dose of MECA, NIC, and placebo will require three challenge days for each participant.

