### Statistical Analysis

**Analyses for Working Memory Performance Hypothesis Testing (H1a and H2a):** Comparisons of **MECA to placebo** will be conducted in support of **Hypothesis 1a**, while similar analyses comparing **NIC to placebo** will be used to test the hypotheses associated with **Hypothesis 2a**. The overall statistical model is:  $Y_{ijk} = \mu + s_{ik} + \pi_j + \tau_{t[i,j]} + \lambda_{d[i,j-1]} + x_k + \varepsilon_{ijk}$ , where  $Y_{ijk}$  is the value of the outcome of interest (**derived from the performance data described here and imaging data described below**) in subject k in sequence i at period j,  $\mu$  is the overall mean of the outcome of interest;  $s_{ik}$  is the effect of subject k in sequence i,  $i=1, 6$ ;  $\pi_j$  is the effect of period j,  $j=1, 3$ ;  $\tau_{t[i,j]}$  is the effect of treatment t,  $t=1, 2$  in period j of sequence i;  $\lambda_{d[i,j-1]}$  is the carryover effect of the treatment administered in period  $j_1$  of sequence i, where  $\lambda_{d[i,0]}=0$ ;  $x_k$  is the effect of baseline covariates for subject k; and  $\varepsilon_{ijk}$  is the random error (Jones and Kenward 2015). Because of the possibility of missing values in some of the measurements, we will employ a mixed effects model for these analyses, relying on the SAS proc mixed procedure for these analyses (Brown and Prescott, 2006).

**For this model, the effects of  $s_{ik}$  (subject) and  $\varepsilon_{ijk}$  (error) are considered random; all other effects are fixed.**

We will directly examine the effects of the drugs in older adults compared to younger adults. The mixed effects model will be adapted by the inclusion of additional variables to account for the effect of age group ( $g_{il}$  the effect of subject i in age group l; l=younger, older) and the treatment-by-age group interaction ( $g_{il} * \tau_{t[i,j]}$ ). The effect of interest in these analyses will be the interaction, which will test whether the effects of MECA or NIC differ with respect to the age of the subject. We predict there will be a significant interaction and will examine the age differences in response to the challenge drugs. For **performance analyses,  $p<0.05$**  will be used for statistical significance. We have used similar models in our prior work ([name] et al. 2012; [name] et al. 2009).

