**Sample Size Calculations:** The sample size calculations are based on pilot data collected in our laboratory in separate studies: 1) older women with MECA and placebo challenges 2) younger adults during NIC and placebo challenges, and 3) older and younger adults with no challenge. We assume that, while the **fMRI** changes in younger adults will be in the same direction as older adults, the magnitude of the changes will be smaller. fMRI performed in younger adults during a 3-back condition showed a mean beta value of -1.12 in the **MFG**, compared to a mean of -0.54 in older adults. We assume that the MECA challenge in the younger adults will increase activation to a mean beta value mimicking that of the older adults on placebo (-0.54), while older adults will have an even greater activation increase to a mean beta of 1.00. Assuming a standard deviation of 0.40, a correlation of 0.35, both calculated from our pilot data, and a Type I error rate of 0.001, 13 subjects will provide 90% power to detect differences between younger and older adults in this region after MECA compared to placebo. A sample size of 19 younger adults and seven older adults will provide greater than 90% power to detect the within-group differences as statistically significant.

For **working memory performance**, sample size calculations are based on a Type I error rate of 0.05. The mean proportion correct for the 3-back performance in older adults was 0.75 compared to a mean of 0.88 in the younger adults, with a standard deviation of 0.13. We predict that the effect of the **MECA** challenge will be to reduce this accuracy measure in both the younger and older adults, with the older adults proportion correct decreasing to 0.60 while the decrease in younger adults will be less severe, decreasing to 0.83. Assuming a correlation of 0.35 a total of **48 subjects** will provide 90% power to detect differences on this test with MECA compared to placebo. This sample size will be sufficient to provide 90% power to detect a statistically significant decrease in performance among the older adults.

Consistent with our results of younger adults following **NIC** challenge, we assume that the effects of this stimulation will be in the opposite direction but similar in magnitude to those outlined above. We assume approximately a 20% drop-out rate; therefore, we will recruit 56 subjects/group, with the goal of **48 subjects/age group** completing the study.

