For the correlational analyses, 48 subjects in each group will provide 90% power to detect a correlation of 0.46 as statistically significant and 80% power if the statistically significant correlation coefficient is 0.41.

**Risks/Benefits:** *Describe any potential or known risks. This includes physical, psychological, social, legal or other risks. Estimate the probability that given risk may occur, its severity and potential reversibility. If the study involves a placebo or washout period, the risks related to these must be addressed in both the protocol and consent. Describe the planned procedures for protecting against or minimizing potential risks and assess their likely effectiveness. Where appropriate, discuss plans for ensuring necessary medical or professional intervention in the event of adverse effects to the subjects. Discuss the potential benefits of the research to the subjects and others. Discuss why the risks to the subjects are reasonable in relation to the anticipated benefits to subjects and others. Discuss the importance of the knowledge gained or to be gained as a result of*

*the proposed research and why the risks are reasonable in relation to the knowledge that reasonably may result. If there are no benefits state so.*

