## SUBJECT CHARACTERISTICS, IDENTIFICATION AND RECRUITMENT

**Subject Selection:** Provide rationale for subject selection in terms of the scientific objectives and proposed study design.

**Participants:** In order to complete testing on 48 **non-smoking** healthy older adults, aged 65-75 years and 48 **non-smoking** healthy younger adults, aged 21-30 years, we will screen 58 potential participants in each age group for a total of 116. An equal number of men and women will be recruited. During the drug challenge phase of the study younger female participants will be tested in the follicular phase of their menstrual cycles and will have a negative pregnancy test before each session. The older adult group will be carefully screened using a neuropsychological assessment (below) to ensure they do not have MCI or pre-MCI. In both age groups, we anticipate a dropout rate of approximately 20%, as has been our experience in our prior studies. We aim to have 48 older and 48 younger participants complete the study for a total of 96 participants.

**Cognitive/Behavioral Screening:** All **older participants** will be cognitively and behaviorally assessed using standard tests designed to exclude participants with significant cognitive or behavioral impairment including the Mini Mental State Exam (MMSE) (Folstein et al. 1975), Brief Cognitive Rating Scale (Reisberg et al. 1993b), the Mattis Dementia Rating Scale (Jurica et al. 2001), and the Global Deterioration Scale (GDS) (Reisberg et al. 1993a). Participants will be required to have a GDS score of 1-2, a MMSE score of greater than or equal to 27, and score above 130 on the Mattis scale. Older participants will have an informant complete the Informant Questionnaire on Cognitive Decline in the Elderly (IQCODE; Jorm 2004) and have scores of 3 or less indicating no cognitive change.

**All older and younger participants** will undergo the following behavioral screening measures: a Structured Clinical Interview for DSM-IV-TR (SCID) (First et al. 2001) to establish the presence/absence of Axis I psychiatric disorders, and the Beck Depression Rating Scale (BDI, score < 10) (Beck et al. 1961). Participants will be excluded if they have a current Axis 1 disorder. All participants will perform the Wechsler Abbreviated Scale of Intelligence (WASI) to assess IQ and will be required to score above 80.

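### The 56 recruits per age group do not follow from 20% dropout and 48 completers (60 would), and the 48 in the performance power sentence is a per-group figure; the power effect of 56 instead of 60 is small

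*Combined protocol and SAP*

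**What the plan says.** Three parts of the protocol give sample-size counts.

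- **Statistical Considerations, Sample Size Calculations (performance).** With a Type I error rate of 0.05, the plan says that "a total of 48 subjects will provide 90% power to detect differences on this test with MECA compared to placebo". The paragraph ends with the recruitment number: "We assume approximately a 20% drop-out rate; therefore, we will recruit 56 subjects/group, with the goal of" 48 per age group finishing the study. The correlation paragraph that follows is explicitly per group: "48 subjects in each group will provide 90% power to detect a correlation of 0.46 as statistically significant".
- **Subject Selection and Number of Subjects.** Both sections say "we will screen 58 potential participants in each age group for a total of 116", and both repeat the dropout assumption: "we anticipate a dropout rate of approximately 20%, as has been our experience in our prior studies". Both aim for 48 older and 48 younger completers, 96 in all.
- **Procedures, Medical Screening.** Screening comes before the challenge days: "Once a participant passes the screening, s/he will be scheduled for" the three challenge and scan days.

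For the performance outcomes, the Statistical Analysis section names the treatment-by-age-group interaction as the effect of interest. It also says: "Because of the possibility of missing values in some of the measurements, we will employ a mixed effects model for these analyses".

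**The concern.** The recruitment sentence presents 56 as the consequence of 20% dropout and 48 completers, and it is not. If recruitment stops at 56 and dropout is 20%, the trial should expect to fall short of its completer target in both age groups. Read literally, the power sentence describes a study half the intended size. The 58 to be screened sits beside the same dropout rate and the same 48 completers, and nothing links it to the 56. At stake are whether the trial can expect the completers its power statements assume, and whether a reader can tell which count is intended.

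**Working it through.** **Inputs, all from Sample Size Calculations.** 3-back proportion correct on placebo: older 0.75, younger 0.88. On mecamylamine: older 0.60, younger 0.83. SD 0.13, within-person correlation 0.35, alpha 0.05, power 90%. The plan does not state sidedness or method. I use a two-sided test, because a one-sided test would need only 38 to 39 per group.

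**1. Reproducing the 90% power.**

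- Difference between the age groups in mean change: (0.75 − 0.60) − (0.88 − 0.83) = 0.10.
- SD of a within-person change: 0.13 × √(2 × (1 − 0.35)) = 0.1482.
- Standardised effect: 0.10/0.1482 = 0.675.
- Noncentrality with n per group: 0.10/(0.1482 × √(2/n)). For n = 48 this is 3.305; for n = 24 it is 2.337.

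| n per age group | Power, noncentral t | Power, normal approximation |
|---|---|---|
| 24 (48 in total) | 62.9% | 64.7% |
| 45 | 88.6% | 89.3% |
| 46 | 89.3% | 89.9% |
| 47 | 89.9% | 90.5% |
| 48 | 90.5% | 91.1% |

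By the t calculation, 48 per group is the smallest size that reaches 90%. The plan's figure therefore reproduces as a per-group number. The fMRI figure of 13 behaves the same way: a difference in change of 1.54 − 0.58 = 0.96, SD of change 0.40 × √1.30 = 0.456 and alpha 0.001 give 92.8% power with 13 per group and 88.9% with 12.

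**2. Dropout.**

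- Recruits needed for 48 completers: 48/(1 − 0.20) = 60.
- Completers expected from 56: 56 × 0.80 = 44.8.
- Dropout at which 56 gives 48: 1 − 48/56 = 14.3%.
- Chance of at least 48 completers, with independent 20% dropout: from 56 recruits, 18.5% in one group and 3.4% in both; from 60 recruits, 57.6% and 33.2%.

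**3. The 58.**

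- Screen failures allowed if 56 are to be recruited: 58 − 56 = 2 per group, or 2/58 = 3.4%.
- Completers with no screen failures: 58 × 0.80 = 46.4.
- Multiplying up instead of dividing, 48 × 1.20 = 57.6, rounds to 58. That may be where 58 came from, but it does not deliver 48 completers.
- The documents give no screen-failure rate. As an assumption only, rates of 10%, 20%, 30% and 40% among 58 screened, followed by 20% dropout, leave about 41, 37, 32 and 27 completers per group (rounded down), with power of about 86%, 82%, 76% and 68%.

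**4. What 45 instead of 48 completers costs.**

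- Performance interaction, completers only: 90.5% falls to 88.6%.
- Partial data in the mixed model, starting from 56 (44.8 completers and 11.2 dropouts per group): 88.5% if dropouts contribute nothing; 90.0% if all leave after session 1 (equivalent to 47.2 completers); 92.3% if all leave after session 2 (equivalent to 51.3). This assumes compound symmetry, data missing at random, six balanced sequences with period effects, and no carryover term.
- Correlations by Fisher z at n = 45: 89.7% power for r = 0.46 and 80.6% for r = 0.41, against 91.6% and 83.2% at n = 48.
- Mecamylamine decrease within older adults: 0.15/0.1482 = 1.012, with power above 99.9% at n = 45.

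**The case against.** **The target is completers.** The design section plans to enrol and complete 48 per group, nothing says recruitment stops at 56, and the dropout rate is only approximate. This is fair: a shortfall arises only if 56 is a cap and dropout really is 20%. But 14.3% is too far from 20% to pass as rounding, the plan cites 20% as its own prior experience, and it gives no lower rate.

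**The rest of the plan settles the word total.** Every other section uses 48 per group, and the sentence after the power claim applies the same sample size to older adults alone. Nobody following the plan would enrol 24 per group. The sentence also does not name the interaction: read as a pooled mecamylamine-placebo comparison in 48 people (mean change 0.10, SD 0.1482), power would be about 99.6%. I accept that this is a wording error and not a design error. The interaction reading is an inference, but it is the effect of interest named in the analysis section, and the stated 90% reproduces under it at 48 per group.

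**The 58 may not be a true screening count.** Number of Subjects is where the form asks for anticipated enrolment, and 58 may be a second dropout-inflated figure. The documents do not settle this. On that reading the allowance of two screen failures does not apply, but 58 still yields only 46.4 completers at 20% dropout and still differs from 56 without explanation.

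**Conclusion.** The point holds and is minor. At the stated dropout rate, 60 recruits per group, not 56, are needed to expect 48 completers. The 90% power for performance belongs to 48 per age group. Taking 56 as a cap and 20% dropout as true, the interaction loses about 2 power points on completers, and possibly nothing once the mixed model uses partial data. The correlation power statements barely move, and no hypothesis or analysis changes.

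That assessment of size covers 56 against 60 only. If 58 is a ceiling on the number screened, the shortfall depends on a screen-failure rate the plan does not give, and it could be larger. That is a further reason to reconcile the counts.

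**What to change.** In Sample Size Calculations, replace the total of 48 with 48 per age group (96 in total). Then choose one of these so that the figures agree:

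- keep 56, and state about 45 expected completers per group with about 88% to 89% power on completers, noting that partial data in the mixed model may recover the difference;
- keep 56, and state a dropout rate of about 14% with support, because the recruitment sections give about 20% as prior experience;
- recruit 60, if 48 completers are to be expected at 20% dropout.

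In Subject Selection and Number of Subjects, say whether 58 counts people screened or people enrolled, and how it relates to the number recruited. If it is a screening count, state the screen-failure rate it assumes.

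Keeping 56 costs only protocol wording, and that is enough to resolve the point. Moving to 60 adds 4 people per group, 8 in all: at most 8 × 3 = 24 challenge and scan days and at most 8 × $400 = $3,200 in payments (less where payment is pro-rated), plus extra screening that the documents do not cost. Even then, 60 gives 48 completers on average and not with certainty.

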## **POTENTIAL BENEFITS**

Participants will not necessarily derive any direct benefits from participation in these studies other than the monetary remuneration for their time. It has been the experience of the CNRU that participants may derive psychological benefit and satisfaction from their participation in these types of studies because of the knowledge that their efforts may help future patients. The benefit to society is twofold: the knowledge gained about the nature of the cognitive changes associated with normal aging role of nicotinic cholinergic system in normal aging.

## **Importance of the Knowledge to be Gained**

The benefits to society of greater knowledge about the etiology of the normal cognitive changes in aging and their possible amelioration would appear great. The risks include temporary side effects of the drugs, and as mentioned above, can be monitored and treated appropriately when this kind of study is conducted in a medical environment. When considering increasing older adult population and the increasing cost of care for those not able to live on their own because of debilitating changes in cognitive functioning, the overall the risk/benefit ratio appears to be in favor of conducting these studies.

## **POTENTIAL RISKS**

**MECAMYLAMINE:** Mecamylamine is a centrally and peripherally active non-competitive antagonist of nicotine (and presumably acetylcholine) at C6 (ganglionic) type nicotinic receptors. Mecamylamine was in clinical use as an oral antihypertensive agent in the 1950's and is occasionally used today for autonomic disinhibition following such conditions as spinal cord injury. Peak cognitive and physiologic effects appear to occur by 2-3 hours and dissipate by 4-6 hours after oral administration. Mecamylamine (administered alone) can cause hypotension, changes in cardiac rate, decreased salivary secretions, decreased gastrointestinal tone and urinary hesitancy. Drs. [name], [name], [name], and [name] have used mecamylamine extensively in clinical studies in identical doses to those proposed here. We have occasionally observed prolonged (>6 hrs) asymptomatic orthostatic hypotension that they have treated conservatively by keeping the subject in bed and giving fluids. No sequelae have been observed and no other significant adverse events have occurred. There have been no clinically significant behavioral changes observed with this drug, and no long-lasting cognitive changes.

**NICOTINE TRANSDERMAL PATCH:** At the nicotine dose proposed in this study, the major peripheral action of nicotine is facilitation of impulses through all autonomic ganglia, stimulation of the adrenal medulla and stimulation of sensory receptors including chemoreceptors in the carotid body. Ganglionic depression occurs at higher nicotine levels. In cardiovascular systems, mild increases in heart rate and blood pressure from sympathetic ganglion stimulation, catecholamine release from adrenal medulla, and aortic and carotid body chemoreceptor stimulation may occur. A mild parasympathetic response may be seen in the gastrointestinal tract and bladder (increased tone and motor activity), with increased secretion of exocrine glands. Nausea and vomiting can occur from peripheral (bowel activity and vagal efferent nerve stimulation) and central (medullary emetic chemoreceptor trigger zone stimulation) causes. Low dose stimulation of the CNS could in theory produce tremors and respiratory stimulation, although this is rarely seen except in patients with tremor disorders. Toxic nicotinic doses result in CNS depression. The most common adverse side effect of the nicotine transdermal patch is skin irritation and accounted for approximately 25 percent of adverse event reports regarding the nicotine transdermal patch to the FDA (Spyker et al. 1998). These effects consist of erythema, pruritus, edema, and rash. The PI and co-investigators have experience in administering transdermal nicotine for over ten years to non-smoking, healthy younger adults, healthy premenopausal women, and older patients with Mild Cognitive impairment. As the participants to be enrolled in this study will be selected for the absence of significant cardiovascular, cerebrovascular disease, or diabetes, we believe that the cardiovascular and cerebrovascular risk profile of transdermal nicotine in such participants is minimal.

**fMRI RISKS:** MRI has no known risks. Participants will be screened for metallic implants or any magnetic devices on or in their bodies prior to inclusion in the study. The MRI scanner produces a loud banging

noise and may be uncomfortable for some people who have claustrophobic-like reactions in confined spaces. Individuals will be allowed to terminate their participation should strong reactions occur. The long-term risks of functional MRI are unknown.

**MRI Safety and the Potential for Hearing Loss:** One potential safety issue in the administration of MR scans is the level of noise. The rapid alternation of currents within the gradient coils causes the coil assemblies to vibrate against their mountings generating a loud resonant noise. The noise may sound like a banging in most cases or even a high pitched whistle with some EPI sequences. Routine clinical sequences generate acoustic noise levels of typically 65-95 dB, but when faster sequences are run the gradients tend to vibrate harder and the noise tends to get louder.

For clinical MRI systems, the FDA currently accepts acoustic noise levels established by the Occupational Safety and Health Administration (OSHA), which indicates that the average noise must remain below 105 dB and the peak acoustic noise must remain below 140 dB. It is also important to consider the duration of noise exposure as this affects the potential for hearing damage. The following table, taken from the OSHA website provides guidelines for maximum decibel levels according to duration of exposure:

Continuous  noise in db (A) measured on slow response	OSHA  maximum exposure per day (hrs)
85	16
90	8
95	4
100	2
105	1
110	0.5
115	0.25

If the variations in noise level involve maxima at intervals  $\leq 1$  sec, it is considered continuous.

Adapted from Table G-16a OSHA Regulations for Noise Exposure 1910.95

Our average research MRI is 60 minutes (or less) in duration, making the maximum acoustic noise level 105 decibels. Previous investigation has established that MRI acoustic noise can cause temporary hearing loss but that this hearing loss can be prevented with earplugs or similar interventions (Brummet et al. 1988). In fact, the study found that threshold changes of 14 patients who received MRIs without hearing protection had returned to within 10dB of baseline within 15 minutes. Those imaged with hearing protection rarely suffered hearing loss and never to the same extent.

A study conducted in 2001 by Price et al. (Price et al. 2001) found that at 1.5T-3T, the highest mean sound pressure levels varied from 103 to 115dB. It is important to note, however, that at UVM/FAHC we follow strict guidelines for the protection of subject hearing. Subjects are required to use both foam earplugs which block 29 dB of sound pressure, and noise attenuating headphones which block 30dB of sound pressure. Wearing headphones and earplugs together do not produce additive effects in hearing protection, but can increase the NRR by an additional 5-6 dB (equivalent to approximately half the sound intensity).

Therefore, the maximum level of sound pressure emitted by a 3T scanner would be 115 dB, reduced by either 30 dB attenuating earphones or 29 dB attenuating foam earplugs, resulting in either 85 or 86 dB of sound pressure. Decibel levels of 85-86 per OSHA guidelines would need to be presented at a continuous duration of more than 8 hours to endanger human hearing (see chart above). Our MRI sessions are generally 60 minutes in length, with frequent breaks: one following each 5-10 minute fMRI task or structural scan. Therefore, it is unlikely that participants under our care would suffer any form of hearing loss, but in rare instances, patients who are particularly susceptible to the damaging effects of loud noises may experience mild or temporary hearing loss.

**PROTECTIONS AGAINST RISK:** In addition to the exclusion criteria outlined above, the following steps will be taken to minimize risk. To enhance the confidentiality of participant data, subjects will be assigned a study number. All data will be kept in locked offices and suites and computerized data will be kept on a secure server.

All participants will be given medication under the close supervision of a physician and research nurse. Participants will be assessed by a research nurse and physician at the completion of each experimental session for residual effects of study medications on cognitive, motor, or cardiovascular functions. A standard field sobriety test will be used to assess motor and/or cardiovascular difficulties. This standardized test is completed at the beginning and end of protocol day and consists of three subtests including visual gaze nystagmus assessment, heel-to-toe walking, and standing on one leg. The participant's score on this test battery must be the same at discharge as at admission. Any participant having residual effects or impairments will be asked to remain in the hospital for observation until such effects dissipate. No prolonged residual effects have been seen in previous studies conducted by the CNRU.

**Therapeutic Alternatives:** List the therapeutic alternatives that are reasonably available that may be of benefit to the potential subject and include in the consent form as well.

